6.2. Preparation, Handling, and Storage

All study medication will be stored in a secure area with restricted access. Capsules must be stored at controlled room temperatures as indicated on the product specific labeling.

The investigator is responsible for ensuring that all study medication received at the site is inventoried and accounted for throughout the study. The dispensing of study medication to the participant, and the return of study medication from the participant, must be documented on the medication accountability form. Participants must be instructed to return all original blister strips, whether empty or containing study medication.

Study medication must be handled in strict accordance with the protocol and the blister label. Unused study medication, and study medication returned by the participant, must be available for verification by the sponsor's study site monitor during on-site monitoring visits. The return to the sponsor of unused study medication, or used returned study medication for destruction, will be documented on the medication return form. When the study site is an authorized destruction unit and study medication supplies are destroyed on-site, this must also be documented on the medication return form.

Study medication should be dispensed under the supervision of the investigator or a qualified member of the study-site personnel, or by a hospital/clinic pharmacist. Study medication will be supplied only to participants participating in the study. Returned study medication must not be dispensed again, even to the same participant. Study medication may not be relabeled or reassigned for use by other participants. The investigator agrees neither to dispense the study medication from, nor store it at, any site other than the study sites agreed upon with the sponsor.

6.3. Measures to Minimize Bias: Randomization and Blinding

Procedures for Randomization

Central randomization will be implemented in this study. Subjects will be randomly assigned to one of two treatment groups based on the first of two computer-generated randomization schedules prepared before the study by, or under the supervision of the sponsor.

The randomization will be balanced by using randomly permuted blocks stratified by lead-in response status and anhedonia (SHAPS total score <20 vs \geq 20).

Exact timing of randomization for each subject will be blinded. The interactive web response system (IWRS) will assign a unique treatment code, which will dictate the treatment assignment and matching study drug kits for the subject. The requestor must use his or her own user identification and personal identification number each time when contacting the IWRS, and will then give the relevant subject details to uniquely identify the subject.

Blinding

Blinded treatment will be used to reduce potential bias during data collection and evaluation of clinical endpoints.

The investigator will not be provided with randomization codes. The codes will be maintained within the IWRS, which has the functionality to allow the investigator to break the blind for an individual subject.

Data that may potentially unblind the treatment assignment (e.g., study medication plasma concentrations, plasma biomarkers) will be handled with special care to ensure that the integrity of the blind is maintained and the potential for bias is minimized. This can include making special provisions, such as segregating the data in question from view by the investigators, clinical team, or others as appropriate until the time of database lock and unblinding. Also, the site staff should not discuss insights on unblinding of randomization with the subjects.

Under normal circumstances, the blind should not be broken until all subjects have completed the study and the database is finalized. The investigator may in an emergency determine the identity of the treatment by contacting the IWRS. While the responsibility to break the treatment code in emergency situations resides solely with the investigator, it is recommended that the investigator contact the sponsor or its designee if possible to discuss the particular situation, before breaking the blind. Telephone contact with the sponsor or its designee will be available 24 hours per day, 7 days per week. In the event the blind is broken, the sponsor must be informed as soon as possible. The date, time, and reason for the unblinding must be documented in the appropriate section of the electronic case report form (eCRF), and in the source document. The documentation received from the IWRS indicating the code break must be retained with the subject's source documents in a secure manner. Subjects who have had their treatment assignment unblinded should continue to return for required follow-up evaluations.

In general, randomization codes will be disclosed fully only if the study is completed and the clinical database is closed. However, if an interim data review by an unblinded reviewer is specified (see Section 7.1), the randomization codes and, if required, the translation of randomization codes into treatment and control groups will be disclosed to those authorized and only for those subjects included in the interim review.

6.4. Study Medication Compliance^a

Study medication will be taken at home by the subject. The first dose will be taken by the subject on Day 2 of the study at home.

Dosing will be documented by app's using the subjects' smartphone, or on a smartphone provided to the subject if they are unable to use their own. The Q1.6-app will present an electronic diary asking subjects to confirm dosing of study medication. When available, also a medication adherence monitoring platform (AiCure®-app) will be used. The Platform uses artificial intelligence on smartphones to visually confirm proper medication administration and ingestion of the study drug in real time without human intervention. Video recordings of the drug intake are also recorded and stored to AiCure's secure server for further analysis to reconfirm proper medication administration, to identify any usability issues or intentional non-adherence, and to check for duplicate enrollment. In addition, built-in reminders and a communication system allow real-time intervention by study personnel in case of improper drug administration or interruptions by the subject.

When in the clinic, study medication will be self-administered on site as outlined in Section 6.1. The administration of study medication will be witnessed by the investigator or a properly trained designee. The exact date and time of drug administration will be recorded in the eCRF.

The investigator or designated study personnel will maintain a log of all study drug dispensed and returned. Drug supplies will be inventoried and accounted for throughout the study.

If appropriate, additional details may be provided in a pharmacy manual/study site investigational product manual that is provided separately and noted in Section 8.1, Study-Specific Materials.

6.5. Concomitant Therapy^b

All prestudy therapies administered up to 30 days before screening must be recorded at screening (and confirmed by treating physician).

JNJ-67953964 is primarily metabolized by CYP3A. Subjects should not use medications that are moderate or strong CYP3A inhibitors or inducers from 14 days or at least 5-times the drug's half-life (whichever is longer) prior to study drug administration until the last study visit. The prohibited medications include but are not limited to: CYP3A inhibitors such as systemically

^a This section has been amended by amendment INT-1

^b This section has been amended by amendment INT-2

administered erythromycin, clarithromycin, ketoconazole or itraconazole, and CYP3A inducers such as rifampin. Similarly, subjects should avoid consumption of grapefruit, grapefruit juice and Seville oranges (including orange marmalade) and herbal products containing St. John's wort, ephedra, ginkgo, ginseng, or kava. Appendix 5 includes examples of concomitant drugs to be avoided (moderate or strong inhibitor/inducer of CYP3A4).

Subjects will be enrolled contingent on having initiated SSRI/SNRI antidepressant treatment for their current episode of MDD. The following antidepressants are permitted: citalopram, escitalopram, sertraline, paroxetine, venlafaxine (XR), desvenlafaxine, fluoxetine, duloxetine, milnacipram, vilazodone, levomilnacipran and vortioxetine. Fluvoxamine is a CYP3A4 inhibitor and will not be allowed in this study. Subjects will only continue one of these allowed antidepressants at an adequate and tolerated dose (i.e. monotherapy) during the study. No changes in the antidepressant or dose are permitted from screening until the end of the study.

For safety reasons, the use of hypnotic drugs or food supplements should be limited from the baseline visit (Visit 2) until the last study visit (may be tapered during screening period). However: Nonbenzodiazepines sleep aids (including: zolpidem, zaleplon, and eszopiclone) are allowed on a PRN basis during the study but NOT within 24 hours before being in the clinic and not more than 2 nights in a row.

Prohibited (from baseline and throughout the study) hypnotic drugs or food supplements include but are not limited to:

- Benzodiazepines when used only as needed (PRN) are not allowed. A subject may continue to take a benzodiazepine treatment only if:
 - The subject has been taking a stable daily dose for at least 6 weeks prior to screening.
 - The dose does not exceed an equivalent of 2 mg of lorazepam per day.
 - Allowed benzodiazepines are lorazepam (≤ 2 mg/day), clonazepam (≤ 0.5 mg/day) and alprazolam (≤ 1 mg/day) being taken daily. Other benzodiazepines should be discussed before subject enrollment with the study responsible physician.
 - Treatment will be continued unchanged during the study.
- Sedating antihistamines
- Continuous use of zolpidem, zopiclone, eszopiclone and ramelteon
- SAMe
- Melatonin, agomelatine.

Subject should also not use the following medication from screening and throughout the study:

- MAOIs from 12 weeks before screening.
- Opioids from 2 weeks before screening.
- Psychostimulants such as methylphenidate or dextroamphetamine within 2 weeks before screening.

- Psychotropics with antidepressant effects such as atomoxetine or thyroid supplementation, in addition to their SSRI or SNRI treatment within 2 weeks before screening.
- Antipsychotic drugs (D₂-antagonists), lithium and other mood stabilizers from 2 weeks before screening. However, Seroquel (quetiapine) in a dose ≤ 100 mg is allowed when used in a stable dose for at least 8 weeks prior to screening. Quetiapine treatment should be continued unchanged during the study.
- Trazodone for treatment of insomnia in a dose ≤ 100 mg when used for at least 8 weeks at a stable dose will be allowed.

If the administration of any concomitant therapy becomes necessary, it must be reported in the appropriate section of the CRF.

The sponsor must be notified in advance (or as soon as possible thereafter) of any instances in which prohibited therapies are administered.

6.6. Intervention After the End of the Study

Investigators may re-contact the subject to obtain follow-up information regarding the subjects' safety if there are any safety concerns at the last study visit.

Participants will be instructed that JNJ-67953964 will not be made available to them after they have completed/discontinued the study. Subjects should continue taking the SSRI/SNRI they were using during the study until such time as changes in their treatment are recommended by their treating physician. If the subject has persistent symptoms of depression at the completion of the study and has no access to a primary physician or psychiatrist, the investigator should ensure appropriate medical care for the subject after completion of the study.

7. DISCONTINUATION OF STUDY TREATMENT AND PARTICIPANT DISCONTINUATION/WITHDRAWAL

If a participant discontinues study medication or withdraws from the study before the end of the double-blind phase, the early withdrawal assessments should be obtained.

7.1. Unblinded Data Review

Continuous or periodic blinded safety reviews will be done by the SRP. An unblinded review of the data will be conducted if there are safety concerns from this blinded review as a result of severe, serious or unexpected AEs that are at least possibly related to the study drug. This review will be done by a DRC. A DRC will consist of at least one medical expert in the relevant therapeutic area and at least one statistician; committee membership responsibilities, authorities, and procedures will be documented in its charter.

7.2. Completion

A subject will be considered to have completed the study if he or she has completed the 11-weeks of treatment and the assessments at Week 11 (Visit 11) of the study. Subjects who

prematurely discontinue study treatment for any reason before completion of the study will not be considered to have completed the study.

7.3. Participant Discontinuation/Withdrawal from the Study^a

A participant will be withdrawn from the study for any of the following reasons:

- The investigator or sponsor believes (e.g. that for safety or tolerability reasons such as a SAE at least possibly related to the study drug) it is in the best interest of the subject to discontinue the study.
- Increased or intolerable symptoms of depression
 - At the discretion of the investigator after the subject reported a “much worse” or “very much worse” condition using the self-assessment of treatment experience or
 - $\geq 30\%$ increase of MADRS score (compared to Visit 2) during the double-blind treatment period.
- The subject becomes pregnant.
- A subject will be discontinued from the study if the QTcF interval is higher than 500 msec or is prolonged >60 msec from the baseline value. QTc interval prolongation should be confirmed by collecting 2 additional ECGs as soon as possible after the initial ECG. The average value of the QTcF interval of the three ECG's will be used to determine whether a subject should be discontinued. If the QTcF is not readily available, the QTcB may be used instead. The subject will continue to be monitored (maximum 12 hours) by repeated 12 lead ECGs (at least every 60 minutes) until the ECG normalizes.
- A subject who shows signals of clinically meaningful acute suicidal ideation at any time during the study should be withdrawn from the study and referred for appropriate medical/psychiatric care.
- A subject will be discontinued from the study if the liver function tests exceed the values as presented in Section 10.7.

Also, a participant will be automatically withdrawn from the study for any of the following reasons:

- Lost to follow-up
- Withdrawal of consent. When a subject withdraws consent, effort should be made to determine if the cause of withdrawal was due to tolerability or lack of efficacy.
- Noncompliance to take the study medication. Noncompliance will be decided on a case-by-case basis depending on the number of missed capsules and the interval between missed doses.

Subjects who drop out, other than for safety reasons related to the study drug or study procedures, will be replaced if the number of subjects completing the study will be below 96. A maximum of 32 subjects (1/3 of targeted subjects) will be allowed to be replaced. Replacement

^a This section has been amended by amendment INT-3

subjects will receive a new subject ID-number and will be assigned to a new randomization code in the IWRS.

When a subject withdraws before completing the study, the reason for withdrawal is to be documented in the eCRF and in the source document. Study drug assigned to the withdrawn subject may not be assigned to another subject.

Any subject who withdraws after receiving the study drug will have an early withdrawal evaluation as described in Section [8.2.4](#).

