In Study LAFC, 21 AEs were reported by 11 of 13 subjects; none of the AEs was considered by the investigator to be related to JNJ-67953964. Most AEs in these 3 Phase 1 studies were of mild to moderate severity.

In the 3 Phase 1 studies, there were no overall trends in mean clinical laboratory data. Six subjects experienced transient increases in liver function enzymes:

- Study LAFA: 1 subject experienced ALT and AST $>2 \times$ ULN after a single dose of 4 mg, not considered to be related to study drug. Both AST and ALT returned to normal values within 4 days.
- Study LAFB: 5 subjects experienced increases in AST and/or ALT: 2 on placebo and 3 on 10 mg JNJ-67953964. All subjects had normal values at the end of the 14-day treatment period with study drug, which had been administered in combination with alcohol. All elevations were reported 2 weeks after the last dose of study drug and returned to normal within up to 17 days. Most of the elevations of AST and/or ALT remained below 2 \times ULN. Only one subject treated with JNJ-67953964 experienced ALT 6.8 \times ULN and one subject treated with placebo experienced AST 3.2 \times ULN.

No clinically significant changes were observed in, prolactin, and luteinizing hormone. There were no clinically significant changes in vital signs and electrocardiograms (ECGs), including no evidence of QTc prolongation. In Study LAFB, cortisol ratios (concentrations normalized to predose) declined less on Day 1 in subjects who received 10 mg or 35 mg doses, 2 to 8 hours after dose compared to placebo controls (n=2 for 10 mg, n=6 for 35 mg). This was not seen on Day 14. There was no effect on adrenocorticotrophic hormone (ACTH).

In Study D, the compound was well tolerated. The most common AEs were transient mild pruritus, 'modestly positive' mood changes, somnolence and abdominal discomfort.

A total of 71 subjects were randomized in study E, of which 62 (87%) received at least one dose of 15 mg JNJ-67953964 and 67 (94%) received at least one dose of placebo. JNJ-67953964 was generally well tolerated with AEs that were mostly considered mild in severity. There were no discontinuations due to AEs, and there were no SAEs. Fifteen (21%) subjects discontinued the study, 13 subjects (18%) discontinued in Period 1 and 2 subjects (3%) discontinued in Period 2 of the study. Two subjects on placebo discontinued due to AE.

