5.2. Inclusion Criteria^a

Each potential subject must satisfy all the following criteria to be enrolled in the study.

1. Subjects must be men or women, 18 to 64 years of age, inclusive.

Note: Subjects should be at least 18 years of age or older as per the legal age of consent in the jurisdiction in which the study is taking place.

2. Have a Body Mass Index (BMI) between 18 and 35 kg/m² inclusive (BMI = weight/height²).
3. Subjects must be medically stable based on clinical laboratory tests, medical history, vital signs, and 12-lead ECG performed at screening and baseline (Visit 2) For clinical laboratory tests only screening results will be considered. If the results of the serum chemistry panel, hematology, or urinalysis are outside the normal reference ranges, retesting of an abnormal lab value(s) that may lead to exclusion will be allowed once during the screening phase. In 12-lead ECG, QTcF should be \leq 450 msec for males or \leq 470 msec for females and

^a This section has been amended by amendment INT-2 and INT-3.

PR-interval < 220 msec at screening. A retest of an abnormal ECG value will be allowed once in the screening phase. Blood pressure will be the average of 2 measurements.

The subject may be included only if the investigator judges the abnormalities or deviations from normal to be not clinically significant or to be appropriate and reasonable for the population under study. This determination must be recorded in the subject's source documents and initialed by the investigator.

4. Criterion modified by Amendment INT-3.

4.1. Population specific:

- Subjects must have a primary Diagnostic and Statistical Manual of Mental Disorders 5th edition (DSM-5) diagnosis of MDD. Subjects with a diagnosis of comorbid Generalized Anxiety Disorder (GAD), Social Anxiety Disorder (SAD), or Panic Disorder may be included, if the investigator considers MDD to be the primary diagnosis (confirmed by an independent central rater through review of the MINI interview obtained by the site at screening). The current episode should be less than 18 months.
- Subjects must be currently treated with an SSRI/SNRI antidepressant approved in this protocol (see Section 6.5) at an adequate dose, as defined by the ATRQ, and for at least 6 continuous weeks but not more than 12 months.

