7.4. Protocol Stopping Criteria

Blinded medical monitoring by the sponsor will occur on a continuous basis including laboratory and ECG data. When there is any concern about the safety of the participants as a result of severe or serious AEs that are at least possibly related to JNJ-67953964 or if the frequency of discontinuations due to TEAEs exceeds 10% of subjects, an unblinded review of the safety data will take place drug (see Section [7.1](#)). The study will be stopped at any time if safety concerns are related to JNJ-67953964 as per the reviewers' decision. The principal investigator may decide to stop study participation at any time when he/she estimates there is an acute risk for his/her subjects in study.

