8.4.3. Electrocardiogram (ECG)

Twelve-lead ECGs, intended for safety monitoring, will be recorded supine (following 5 minutes rest) so that the different ECG intervals (RR, PR, QRS, QT) can be measured at multiple time points at screening and during the study (see TES). The ECG will be recorded until 4 regular consecutive complexes are available in good readable quality.

During the collection of ECGs, subjects should be in a quiet setting without distractions (e.g., television, cell phones). Subjects should rest in a supine position for at least 5 minutes before ECG collection and should refrain from talking or moving arms or legs. If blood sampling or vital sign measurement is scheduled for the same time point as ECG recording, the procedures should be performed in the following order: ECG, vital signs, blood draw. Please note that fasting blood draw may precede the ECG and vital signs in this study.

Hot and cold drinks and food should be avoided 30 minutes before an ECG measurement whenever possible.

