A listing of subjects with any laboratory result outside the reference ranges will be provided.

ECG

Heart rate and ECG intervals (RR, PR, QRS and QT) as well as corrected QT intervals according to Bazett's formula (QTcB) and Fridericia's formula (QTcF) (Bazett 1920, Sagie 1992, Hodges 1983, International Conference on Harmonization [ICH] 2005) from the 12-lead ECG will be summarized at baseline and at each scheduled time point and for changes from baseline using descriptive statistics.

The number and percentage of subjects with at least one occurrence of a treatment-emergent potentially clinically important QTc measurement (QTc value >450 , >480 , or >500 msec) or with a change from baseline in QTc >30 msec or 60 msec, will be summarized by treatment group.

Data listings of subjects with any potentially clinically important values or with a change from baseline in QTc will be provided.

Vital Signs

Descriptive statistics of temperature, pulse, and blood pressure (systolic and diastolic) values and changes from baseline will be summarized at each scheduled time point. The percentage of subjects with values beyond clinically important limits will be summarized.

Physical and Neurological Examinations

Subjects with abnormal findings will be presented in a data listing.

Other Safety Measures

C-SSRS

The suicidal ideation and behavior data collected from the C-SSRS will be summarized descriptively at each scheduled timepoint by treatment group. Data from the subjects with suicidal ideation and behavior will be presented in data listing.

ASEX and KSS

Sexual dysfunction and KSS data collected will be summarized descriptively at each scheduled timepoint by treatment group.

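### The QTc withdrawal rule is set on QTcF but lets QTcB be read against the same limits, so a subject's heart rate can decide a borderline withdrawal

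*Protocol*

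**What the plan says.** Section 7.3 of the protocol makes discontinuation mandatory "if the QTcF interval is higher than 500 msec or is prolonged >60 msec from the baseline value". A prolonged QTc on one ECG is confirmed with two further ECGs, and "The average value of the QTcF interval of the three ECG's will be used to determine whether a subject should be discontinued". The next sentence is the fallback: "If the QTcF is not readily available, the QTcB may be used instead". It sets no QTcB limit of its own and no heart-rate condition, and it does not say whether the baseline must then also be QTcB.

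Elsewhere the protocol works with QTcF, or keeps the two corrections apart:

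- Section 5.2, inclusion criterion 3, sets ECG eligibility at screening on QTcF alone (at most 450 msec for men and 470 msec for women).
- Section 8.4.3 has ECGs recorded "so that the different ECG intervals (RR, PR, QRS, QT) can be measured at multiple time points".
- Section 9.5 summarizes QTcB and QTcF as separate quantities.

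The SAP covers population PK and exposure-response and does not address this rule.

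**The concern.** Bazett and Fridericia corrections are different functions of heart rate, so one pair of limits cannot mean the same thing on both. Above 60/min QTcB is larger than QTcF, and below 60/min it is smaller. Two subjects with identical QTcF could therefore receive opposite decisions under a mandatory safety rule, depending on heart rate and on which correction the site had to hand.

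The error can go either way: a subject without prolongation may be withdrawn, or a subject who meets the QTcF rule may stay on drug. Averaging three ECGs taken close together does not help, because at a given heart rate the discrepancy is systematic. What is at stake is individual safety decisions, not the efficacy analysis.

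**Working it through.** **Inputs from the protocol.** Limits of 500 msec and a 60 msec rise (7.3). Screening ceilings of QTcF 450 and 470 msec (5.2). Five on-study ECG visits after baseline: Visits 5, 6, 7, 10 and 11 (Time and Events Schedule). 142 entering the lead-in with 10% drop-out (9.1); responders and non-responders are both randomized, so about 142 × 0.90 = 128 are randomized.

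**Formulas.** The protocol names the corrections without printing them; the standard definitions are assumed. With RR = 60/HR in seconds, QTcB = QT/RR^(1/2) and QTcF = QT/RR^(1/3). Hence

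QTcB = QTcF × (HR/60)^(1/6).

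The ratio is 0.970 at 50/min, 1.000 at 60, 1.026 at 70, 1.049 at 80 and 1.070 at 90.

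**Wrong withdrawal, 500 msec limit.** QTcF 470 at 90/min gives QTcB 502.9. It reaches 500 at 60 × (500/470)^6 = 87.0/min. QTcF 450 reaches 500 at 60 × (500/450)^6 = 112.9/min.

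**Missed case, 60 msec limit.** Take QTcF rising from 410 to 475 (+65), which requires discontinuation, while heart rate goes from 70 to 62/min.

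- Baseline QTcB = 410 × (70/60)^(1/6) = 420.7.
- On-study QTcB = 475 × (62/60)^(1/6) = 477.6.
- Change = 56.9 msec, so neither limit is met.

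With a QTcB baseline taken at 70/min, the miss occurs at any on-study rate below 64.4/min. With a QTcF baseline it needs a rate below 60 × (470/475)^6 = 56.3/min. Using QTcB at both visits therefore does not cure the problem.

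**Missed case, 500 msec limit.** QTcF 505 reads below 500 on QTcB under 60 × (500/505)^6 = 56.5/min; at 50/min it reads 489.9. The 60 msec limit still catches it unless baseline is high: QTcF of about 489.9 − 60 = 430 or more, or about 419 or more if the baseline is QTcB taken at 70/min (429.9/1.026).

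**How often.** The documents give no heart-rate or QTc distribution and no frequency of fallback use, so the following is simulated on assumptions (400,000 subjects):

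- QTcF mean 410, SD 18 between and 8 within subjects, baseline at most 470, no drug effect on QTcF.
- Baseline heart rate mean 70; on-study mean 70, 75 or 80; SD between/within subjects 8/6 or 10/8.
- Same heart rate for the three confirmatory ECGs.
- Fallback used at every ECG. A withdrawal needs the first ECG and the three-ECG average both over a limit.

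Subjects wrongly withdrawn, for on-study mean 70 / 75 / 80:

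| Baseline | SD 8/6 | SD 10/8 |
|---|---|---|
| QTcF | 0.034 / 0.110 / 0.295% | 0.133 / 0.327 / 0.737% |
| QTcB | 0.018 / 0.046 / 0.103% | 0.052 / 0.131 / 0.284% |

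With QTcF throughout there were none. The largest figure is 0.737% × 128 = 0.94 of a subject.

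Share of true 410-to-475 rises read as not meeting the rule, given that the fallback is used:

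| Baseline | SD 8/6 | SD 10/8 |
|---|---|---|
| QTcB | 23.5 / 8.6 / 2.3% | 28.6 / 14.8 / 6.4% |
| QTcF | 8.5 / 3.1 / 0.9% | 14.2 / 7.2 / 3.2% |

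**The case against.** The case for leaving the text alone is that the fallback hardly matters.

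- It is optional and applies only when QTcF is not readily available. If QT and RR are recorded on every ECG, that should be seldom, so simulating it at every ECG gives a ceiling. This stands.
- The top of the wrong-withdrawal range assumes mean heart rate rises from 70 to 80/min. With an unchanged mean of 70 the figures are 0.018% to 0.133%, or 0.02 to 0.17 of 128 subjects. This stands. Section 2.2.2 also reports no clinically significant vital-sign changes in the Phase 1 studies, "including no evidence of QTc prolongation".
- A natural reading is that QTcB replaces QTcF at baseline too. That cuts wrong withdrawals by roughly half or more, but it raises the missed share for the 65 msec rise.
- A 65 msec rise is only 5 msec over the limit. For an 80 msec rise, with QTcB at both visits, the missed share falls to between 0.03% and about 5%; at 90 msec it is about 1% or less. This stands: clear prolongation is nearly always caught.
- Above 60/min the error on the 500 msec limit is on the cautious side. That is true for that limit only; on the 60 msec limit a modest fall in heart rate hides a qualifying rise.
- Section 7.3 also allows withdrawal in the subject's best interest, and under section 7.4 "Blinded medical monitoring by the sponsor will occur on a continuous basis including laboratory and ECG data". Both reduce the harm from a miss, but they rest on judgment rather than on the stated rule.

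These points limit the size of the problem. None makes one pair of limits valid for both corrections.

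**Conclusion.** The concern holds, as a minor one. As written, the fallback can produce a wrong individual decision in either direction. The threshold results follow from the standard formulas and the protocol's own limits. The frequencies rest on assumed distributions: under one wrong withdrawal among about 128 randomized even with the fallback used every time, and a 1% to 29% chance of missing a borderline 65 msec rise when the fallback is used. How many subjects would have such a rise is unknown and probably very few. On QTcF alone, inclusion criterion 3 and section 7.3 are consistent with each other, and the limits themselves are not in question.

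**What to change.** Replace the fallback sentence in section 7.3 with: *If QTcF is not printed by the device, calculate it as QT/RR^(1/3) from the recorded QT and RR (RR in seconds); the discontinuation decision and the baseline it is compared with must both use QTcF.*

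This removes the discrepancy at every heart rate, because any ECG that yields QTcB already holds the QT and RR needed for QTcF. Requiring only the same correction at both visits would not be enough. The cost is one sentence in the protocol and a conversion formula for sites; no extra ECG and no change to the limits are needed.
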